10.1 FACE-Q™: Description

The FACE-Q™ was developed in response to a lack of well-defined and reliable PRO instruments for facial aesthetic patients. It is made up of a set of more than 40 independently functioning scales and checklists measuring concepts and symptoms important to facial

aesthetic patients in relation to different facial areas. The FACE-Q™ can be used with any facial aesthetic patient (surgical and nonsurgical) to measure what patient's think about their appearance, quality of life, adverse effects, and process of care. Each scale provides a standalone score from 0 to 100, with higher scores indicating a better outcome. Depending on the surgical or nonsurgical procedure, only those FACE-Q™ scales and/or checklists relevant to a patient or procedure(s) need be completed.

Primary Efficacy Endpoint is FACE-Q™ Satisfaction with Facial Appearance.

The other efficacy endpoints include the following FACE-Q™ questionnaires;

1. FACE-Q™ Expectations Scale
2. FACE-Q™ Aging Appraisal
3. FACE-Q™ Psychological Function Scale
4. FACE-Q™ Social Function Scale
5. FACE-Q™ Satisfaction with Skin

10.2 Primary Efficacy Parameter

The primary endpoint is the change from baseline in the Rasch-transformed score of the FACE-Q™ Satisfaction with Facial Appearance Overall Scale to the final study visit.

The primary efficacy parameter will be summarized by treatment group and overall, as well as by subgroup being defined in Section 6.3 Subgroup. Two treatment groups are defined as BELKYRA and without-BELKYRA. Overall efficacy is summarized by both groups.

Subgroups of gender and treatment are treated as separate cohorts. There is no between groups analysis to be performed.

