4.1 Study Design Overview

This Phase 4 study is a prospective, interventional, multicenter, combination medical device, drug, and skin care postmarketing study. Each subject will be in the study for up to 11 months depending on the treatments given, and act as his/her own control. All products will be used as per their license only. The investigators will perform all treatments and evaluations.

[figure not shown]
The study is planned to enroll 60 subjects consecutively at approximately 6 study sites in Canada. The ratio of subjects treated with BELKYRA to subjects without BELKYRA treatment will be approximately 1:2 (ie, approximately 20 BELKYRA subjects and 40 subjects without BELKYRA) based on clinical indication and the decision of the subject and investigator. Thus approximately one-third of all subjects will receive BELKYRA treatment. Recruitment will also target men, who are typically under-represented in aesthetic studies.

Detailed descriptions of all study procedures by study visit and study treatment are presented in Table 6.1 and Section 6.

All subjects will sign an informed consent form (ICF) and begin at the screening visit (V0). Subjects receiving BELKYRA treatment will enter the study at V1 continuing on to V12. There will be at least 1 month between repeat BELKYRA treatments and the final BELKYRA treatment.

Subjects not receiving BELKYRA following screening (V0) will enter the study at V7 to begin treatment with Juvéderm HA facial fillers, SkinMedica, and BOTOX Cosmetic, as indicated in the study design diagram (Figure 4.1).

Figure 4.1 Overall Study Design

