11.1.2 Subgroups

Two subgroups will be examined separately:

- Gender: As male and female subjects may have differing expectations/perceptions of aesthetic improvement, they will be examined separately.
- BELKYRA: As it is expected that approximately two-thirds of the enrolled population will not be treated with BELKYRA, subjects treated and not treated with BELKYRA will be examined separately.

Additional subgroup analysis will be discussed in the SAP.

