10 EFFICACY ANALYSES

The primary efficacy endpoint is the change from baseline to the final visit in the overall Rasch-transformed scores of the FACE-Q™ Satisfaction with Facial Appearance Scale. The scale data will be analyzed by using paired t-test. If normality is unmet, Wilcoxon signed-rank test is used to replace paired t-test. If skewness of FACE-Q change from baseline is not close to zero, the change data of FACE-Q is not considered as normally distributed. In this case, one-way nonparametric procedure with Wilcoxon option will be used to replace paired t-test.

One-sample paired t-test is performed on changes at end of study. The following statistics will be provided;

Label of Statistics	Description
N	Number of subjects of overall or a subgroup
Mean	Mean change of FACE-Q™ Scale
SD	Standard deviation of Mean Change
SEM	Standard error of Mean Change
Median	Median of Changes
Minimum, Maximum	Minimum, Maximum (of Changes)
Pr > t	p value of Mean Change through paired t-test, or that of Wilcoxon signed-rank test
95% CIs	95% Confidence Intervals of the Mean, lower and upper limits

The efficacy analyses will be based on the Evaluable population. Baseline for efficacy is defined as the last nonmissing assessment before the first dose of study treatment. All statistical tests will be 2-sided hypothesis tests performed at the 5% level of significance for main effects. All confidence intervals will be 2-sided 95% confidence intervals, unless stated otherwise.

Hypothesis testing will be performed at a 0.05 significance level (2-sided). Since BELKYRA and without BELKYRA are the major treatment cohorts, unless specified, all endpoints will be summarized by those two groups (BELKYRA and without BELKYRA) and overall respectively. However, this study is not designed to compare the efficacy and safety outcomes between subjects treated with BELKYRA and those treated without BELKYRA. All discussion and interpretation related to study outcomes will be mainly focused on the overall results.

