14 DETERMINATION OF SAMPLE SIZE

A sample size of 48 subjects will provide 90% power to detect whether change from baseline to end-of-study visit in the FACE-Q Satisfaction with Facial Appearance Overall Scale Rasch-transformed score is different from zero, assuming a mean change of 12.0 and a standard deviation of 20.0. This calculation is based on a 1-sample, 2-sided t-test at 5% significance level. The assumptions of mean and standard deviation are based on FACE-Q results from Allergan HARMONY Study GMA-CMB-14-001. With a 20% drop-out rate (for early withdrawals and/or subjects who failed to duly complete the FACE-Q Satisfaction with Facial Appearance Overall Scale assessment at end of study), 60 subjects will be enrolled. From the 60 subjects planned to enroll in this study, approximately 20 subjects will be treated with BELKYRA.

Subjects will be assigned to study treatment only if they meet the inclusion criteria and none of the exclusion criteria. Subjects who discontinue treatment will not be replaced.

EXACT software (version 6) was used to confirm the sample size in the protocol.

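### Gender is examined because men and women may differ, but the SAP tests each gender against zero and gives no estimate of the difference, so its subgroup output is easily misread

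*SAP*

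**What the plan says.** Protocol 11.1.2 gives the reason for the gender subgroup: "As male and female subjects may have differing expectations/perceptions of aesthetic improvement, they will be examined separately". SAP 6.3 repeats it. Protocol 4.1 says of enrolment: "Recruitment will also target men, who are typically under-represented in aesthetic studies". Neither document gives a target number or share of men.

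SAP 10.2 summarises the primary endpoint by the subgroups of SAP 6.3, treats gender and treatment subgroups as separate cohorts, and states: "There is no between groups analysis to be performed". The statistics table in SAP 10 covers the overall population or a subgroup. It lists N, mean, SD, SEM, median, range, the 95% CI of the mean, and the "p value of Mean Change through paired t-test, or that of Wilcoxon signed-rank test". SAP 10.3 applies the same methods to five secondary FACE-Q scales.

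Two further statements in Protocol 11.1 and SAP 10 bear on the point. The study is said not to be designed to compare subjects with and without BELKYRA. Discussion and interpretation are to rest mainly on the overall results.

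**The concern.** The reason given for looking at gender is a possible difference between men and women. The only inferential output is one test of change from zero in each gender. Neither test addresses the difference, and a significant result in one group beside a non-significant result in the other is not evidence that the groups differ.

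If men are a minority, as the protocol's own remark on under-representation suggests, the test in men has much less power than the test in women. A treatment that works equally well in both can then readily yield a table that seems to say it works in women and not in men. This can happen on the primary scale and on each of the five secondary scales, and no planned line in the output would correct the impression.

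**Working it through.** **Inputs.** From SAP 14: "This calculation is based on a 1-sample, 2-sided t-test at 5% significance level"; "A sample size of 48 subjects will provide 90% power to detect whether change from baseline to end-of-study visit"; "assuming a mean change of 12.0 and a standard deviation of 20.0"; "With a 20% drop-out rate", giving 60 enrolled. The standardised effect is 12/20 = 0.6. The number of men is an assumption, varied below.

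**The plan's own figure.** Power for n subjects is P(|T| > t(0.975, n−1)), where T is noncentral t with n−1 df and noncentrality 0.6√n. With the stated inputs, 90% power needs 32 subjects, and 48 subjects give 98.3%. The stated pairing of 48 with 90% therefore does not reproduce; an SD of about 25 would give it. The drop-out step does reproduce: 48/0.8 = 60. The mismatch is a separate matter, but it is a reason to run the check at SD 25 as well.

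**Chance of a misleading pattern.** Let the true change be 12 in both genders, with 48 evaluable subjects, m men and w = 48 − m women. Men and women are different subjects, so the two tests are independent:

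P(significant in women, not in men) = power(w) × [1 − power(m)]

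| Men / women | Power, men | Power, women | Women only, SD 20 | Women only, SD 25 |
|---|---|---|---|---|
| 5 / 43 | 18% | 97% | 80% | 75% |
| 8 / 40 | 31% | 96% | 0.959 × 0.688 = 66% | 66% |
| 12 / 36 | 47% | 94% | 0.938 × 0.525 = 49% | 54% |
| 16 / 32 | 61% | 91% | 0.908 × 0.388 = 35% | 42% |
| 24 / 24 | 80% | 80% | 0.804 × 0.196 = 16% | 24% |

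The power columns are for SD 20. If all 60 enrolled were evaluable (SD 20), the chance would be 77% with 6 men, 52% with 12 and 27% with 20. For 80% power in men alone, 24 evaluable men are needed at SD 20, or 37 at SD 25.

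If the signed-rank test replaces the t-test, the smallest possible two-sided p-value with 5 men is 2/2⁵ = 0.0625. Five or fewer men could then never reach 0.05, whatever their responses.

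**What an estimate of the difference would show.** The 95% half-width for men minus women is t(0.975, 46) × 20 × √(1/m + 1/w), with t = 2.013:

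- 8 / 40: 2.013 × 20 × √0.1500 = 15.6 points
- 12 / 36: 2.013 × 20 × √0.1111 = 13.4 points
- 16 / 32: 2.013 × 20 × √0.09375 = 12.3 points
- 24 / 24: 2.013 × 20 × √0.08333 = 11.6 points

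With equal true effects, this interval wrongly excludes zero 5% of the time at any split. Power to detect a true 12-point gender difference is 33%, 42%, 48% and 53% at these four splits, so the interval can serve as an estimate but not as a confirmatory test.

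**The case against.** The strongest reply is that the SAP does what the documents promise. They say the genders will be examined separately. No objective, endpoint or hypothesis asks whether men and women differ. The SAP 10 table also shows N, mean, SD and a 95% CI for each gender, so a small male group would display its own imprecision, and a reader could compute the difference. Interpretation is directed mainly to the overall results, and nothing in the SAP plans a statement that treatment fails in men. In a single-arm study of 60 subjects, a gender contrast would be too imprecise to settle much.

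Most of this stands, and it limits the point to presentation of a subgroup. It does not justify the gender-specific p-values. Low power argues against a test in a handful of men at least as strongly as against a contrast. The instruction on interpretation says mainly, and the p-values would still be produced. The statement that the study is not designed for a comparison names only the BELKYRA groups.

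A reader might infer that men are recruited so that they can be compared with women. The documents do not support that: the reason given is under-representation in aesthetic studies. A reader might also infer that the trial sets itself a gender question and cannot answer it. That goes too far as well, because the rationale mentions a possible difference but commits only to separate examination.

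**Conclusion.** The point holds as a cheap improvement to a subgroup analysis. Separate p-values against zero, without an estimate of the difference, do not bear on the reason given for the subgroup. With identical effects they would show significance in women only 35% to 66% of the time with 16 to 8 men among 48 evaluable. The figure falls to 16% at an even split, so how often the pattern arises depends on men being a clear minority. That is plausible from the protocol's wording but is not stated as a number. The figures also assume the planned change of 12 and SD 20 in both genders; SD 25 leads to the same conclusion.

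The overall primary test and its interpretation are unaffected. The risk is a misread subgroup table and not a wrong primary result.

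It would also be wrong to infer that the BELKYRA groups are descriptive only. Under the SAP 10 table they receive the same p-values against zero. They fall outside this point because the documents say the study is not designed to compare them.

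**What to change.** In SAP 10.2, state that for gender the output will give the already planned mean change with 95% CI in men and in women, without gender-specific p-values, and will add the men-minus-women difference in mean change with its two-sided 95% CI, labelled exploratory. Limit the exclusion of between-group analysis accordingly. SAP 10.3 then carries the change to the five secondary FACE-Q scales.

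The cost is one SAP sentence and one table row per scale, with no additional subjects or data. The downside is an interval that is wide relative to the planned overall change of 12. It should be reported as showing how little can be said about a gender difference, and an interval that includes zero should not be read as evidence that the genders respond alike.

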10.3 Secondary Efficacy Parameters

The same analysis procedures and methods used for the primary efficacy endpoint will be applied for the secondary efficacy endpoints, which include FACE-Q Expectations, FACE-Q Aging Appraisal, FACE-Q Psychological Function Scale, FACE-Q Social Function scale and FACE-Q Satisfaction with Skin.

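### The five key secondary FACE-Q scales are each tested at two-sided 5% in the overall population, with no testing order or adjustment in the readable text.

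*SAP*

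**What the plan says.** SAP 10.1 names one primary endpoint: "Primary Efficacy Endpoint is FACE-Q™ Satisfaction with Facial Appearance". SAP 10.3 then extends its analysis: "The same analysis procedures and methods used for the primary efficacy endpoint will be applied for the secondary efficacy endpoints". It lists five FACE-Q scales: those for skin satisfaction, social function, psychological function, aging appraisal and expectations. Protocol 4.2.2 classes these five scales as key secondary endpoints, together with self-perception of age (SPA).

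The significance level is set once, in SAP 10: "All statistical tests will be 2-sided hypothesis tests performed at the 5% level of significance for main effects". The table of statistics in the same section lists a 95% confidence interval and a "p value of Mean Change through paired t-test, or that of Wilcoxon signed-rank test". Its N row reads "Number of subjects of overall or a subgroup", so the same table is to be filled for subgroups. SAP 10.2 says of the primary: "The primary efficacy parameter will be summarized by treatment group and overall, as well as by subgroup being defined in Section 6.3 Subgroup". The subgroups in SAP 6.3 are gender and BELKYRA use.

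The SAP says so where it does not want tests: SPA (10.3.1), other efficacy endpoints (10.3.2) and safety (11). It says nothing of the kind about the five FACE-Q scales. SAP 10 and protocol 11.1 do state that the study is not designed to compare the BELKYRA groups and that interpretation will rest mainly on overall results.

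**The concern.** Five endpoints carry the label key secondary, and each gets its own p-value and the full 5%. As far as the text can be read, nothing says which is tested first, whether any depends on the primary, or how a lone significant scale should be reported. One scale out of five crossing 0.05 could then be presented on the same footing as the primary.

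This matters because psychological and social function, which the primary objective (protocol 3.1, SAP 5.1) mentions, have dedicated scales only among the secondaries. The objective itself is to be met through the primary satisfaction scale, so the secondaries support the psychosocial message and do not carry it alone. They are still the results most likely to be quoted for it.

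**Working it through.** **Inputs from the documents.** Two-sided 5% per test (SAP 10); five secondary FACE-Q scales (SAP 10.3); 48 evaluable subjects, mean change 12.0, SD 20.0, one-sample t-test, 20% drop-out, 60 enrolled (SAP 14, protocol 11.6).

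**Assumptions, because the documents give no figures.** Correlation between scales: 0 to 0.7. Effect on each secondary scale: the primary's planning value 12/20, with a smaller value shown as well.

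**1. The plan's own figure.** Standardised effect 12.0/20.0 = 0.6; noncentrality 0.6 × √48 = 4.16 on 47 degrees of freedom. Two-sided power at 5% from the noncentral t distribution is 98.3%, not the stated 90%; 90% needs 32 subjects. The step 48/(1 − 0.20) = 60 does reproduce. The gap is a separate matter. Here it means only that there is room for an adjustment.

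**2. Chance of at least one significant secondary if none truly changes.**
- Independent scales: 1 − 0.95^5 = 0.226.
- Equally correlated scales, simulated with n = 48: about 0.21 at correlation 0.3, 0.18 at 0.5 and 0.15 at 0.7.
- If only three of the five are null and independent: 1 − 0.95^3 = 0.143.

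**3. Benefit direction only.** SAP 10.1 says higher scores are better, so a false benefit has probability 0.025 per scale.
- Independent: 1 − 0.975^5 = 0.119.
- Simulated: about 0.10 at correlation 0.3, 0.09 at 0.5 and 0.07 at 0.7.

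**4. With Holm over the five.** Under the same null, an error occurs only if the smallest p-value is below 0.05/5 = 0.01. Independent: 1 − 0.99^5 = 0.049. Simulated: about 0.045, 0.041 and 0.036 at correlations 0.3, 0.5 and 0.7. Requiring a significant primary first can only lower these.

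**5. Power cost at n = 48 (noncentral t).**

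| Assumed effect on a secondary scale | α = 0.05 | α = 0.01 (Holm's first step) |
|---|---|---|
| 12/20 = 0.6 | 98.3% | 92.4% |
| 10/20 = 0.5 | 92.4% | 77.8% |

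The last column is the worst case, since later Holm steps use larger levels. These are powers for the scale's own test; they leave out the condition that the primary succeeds.

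**6. Count of planned p-values.** Six FACE-Q scales × five sets (overall, BELKYRA, without BELKYRA, male, female) = 30: one primary, five overall secondaries and 24 subgroup results. It would be 35 if the transformed PAAQ score is tested. SAP 10.3.2 rules that out, whereas 10.3.2.2 handles the score like the primary.

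**The case against.** Several points against the concern have force.

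- **Missing text.** Protocol 11.4.2, on all other efficacy endpoints, appears in the contents but not in the supplied text, and parts of SAP section 10 are blacked out. A multiplicity rule could stand there. This stands as a caveat, although SAP 10, 10.2 and 10.3, where such a rule would be expected, are readable and have none.
- **Two-sided errors overstate the harm.** An error that matters for a claim is a false benefit, which roughly halves the figure to about 12%. This stands, and both figures are given.
- **Low stakes.** The study is Phase 4, open-label and single-arm, uses licensed products and has one primary endpoint, so its main error rate is already controlled. This stands and limits the weight of the point. It does not tell a reader how to take five p-values on endpoints labelled key.
- **Thirty p-values.** From the count above, a reader might infer that about 30 results could each be taken as proof. The documents do not support that. One of the 30 is the prespecified primary, which needs no adjustment. The 24 subgroup results are already set back by the sentence on overall results and by the absence of any between-group analysis (SAP 10.2). That protection is soft, because it says only mainly, and it does not reach the five secondaries, which are themselves overall results.

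**Conclusion.** The point holds for the five overall key secondary tests. On the readable text, each has a two-sided 5% test with no order, adjustment or descriptive label. If no scale changes, the chance of at least one significant result is 22.6% under independence and about 15-21% at assumed correlations of 0.7 to 0.3; for a false benefit it is about 12% and 7-10% respectively. These rates assume that all five scales are null and, in the correlated cases, equally correlated; with fewer null scales they fall.

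The stronger inference, that the plan invites 30 separate proofs or leaves the psychosocial objective resting on uncontrolled tests alone, is not supported: the primary scale carries that objective and is tested once. The finding is a cheap improvement, not a flaw in the primary analysis.

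**What to change.** In SAP 10.3, state that the five FACE-Q secondary scales are tested only if the primary test is significant, in the overall Evaluable Population, using Holm at two-sided 5%. A prespecified fixed order, each step at 5%, is an acceptable alternative; it costs no power as long as every earlier test succeeds, and testing stops at the first that fails.

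Add that all BELKYRA, without-BELKYRA, male and female results, including their confidence intervals, are descriptive and support no claim of demonstrated benefit. Removing the subgroup p-values alone would not do this, because a 95% interval that excludes zero is the same t-test at 5%.

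If protocol 11.4.2 or the redacted SAP text already holds a rule, refer to it in SAP 10.3.

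The cost is a few sentences and no new data. The downside is power on the secondaries: at Holm's strictest step, 92.4% instead of 98.3% with an effect of 12/20, and a larger loss if a scale's effect is smaller (77.8% instead of 92.4% at 10/20).

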10.3.1 Self-Perception of Age Questionnaire

Subject's assessment of age-related facial appearance by the self-perception of age (SPA) measure at baseline before any treatment to final study visit (V12); responders are defined as having achieved a younger category. No statistical testing will be performed for SPA data distribution.

Summaries of responders are provided in frequency and percentage at baseline and final visit for all three questions (a. I look my current age, b. I look years younger and c. I look years older). A shift table to summarize changes into an improvement category from baseline to the study end is provided in frequency and percentage. No statistical testing for shift tables is performed.

Subgroups in analysis are treated as individual cohorts. No comparison between treatments is performed.

